1.2 Hypotheses

Related to Aim 1, we hypothesize that:

H1: Patients receiving the EMC2 intervention will have better understanding of medication risks than those in the control arm.

H2: Patients receiving the EMC2 intervention will demonstrate safer use of their medication than those in the control arm.

STU#: 00201638

H3: Adverse drug events will have a higher rate of detection for patients in the EMC2 intervention arm than in the control arm.

Related to Aim 3, we hypothesize that compared to usual care, patients receiving the EMC2 strategies will:

H4: Report higher rates of provider Rx counseling

H5: Report higher rates of receipt of print Rx information.

H6: Be more likely to communicate Rx questions.

H7: Report a greater frequency of clinic follow-up.

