Method 2- Each morning, Research Assistants (RAs) at Northwestern University will receive, via file sent to a secure ftp site, a list of patients triggered as eligible during a clinic visit on the day prior. The report will show the information needed to contact the patient and conduct the baseline interview (same data as listed in method 1, plus the name(s) of any study medications prescribed during the visit, the associated sig(s), prescriber name, and regular physician name). With this method, RAs will be able to conduct the baseline interview during the same phone call, immediately after screening and consenting the patient. This method would also allow the RA to explain to the potential participant which of their prescribed medicines would be the subject of the interviews and to confirm that the medication was actually prescribed, eliminating any confusion.

STU#: 00201638

Automatic exposure to part of intervention. Clinics will be randomized either to the intervention arm or to usual care. All patients who see a prescriber at a clinic site randomized to the intervention arm and who receive a prescription for one of the study medications (Table 1) will automatically receive some components of the intervention during their clinic visit (provider counseling, Med Guide Summary), regardless of whether or not they meet further screening criteria. This randomization and recruitment process will ensure that recruited patients may receive all in-clinic EMC2 components on the day they receive a prescription for a study drug. It will also result in a trickle down of some components of the EMC2 Strategy being given to patients seen at the intervention clinic site, but not enrolled in the study for follow-up purposes (EHR tools, but not IVR or nurse follow-up). This specific strategy of “turning on” an EHR intervention with provider or clinic level randomization has been previously approved by the IRB at Northwestern University for three other AHRQ funded grants [P01HS021141-01, 1U19HS021093-01 & 1R18HS017220-01]. Prescribers at these intervention sites will be made aware that the EHR tools have been activated, with the understanding that the tools themselves are educational in nature and will have minimal, if no effect on patient care and clinic workflow.

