3.2 Inclusion and exclusion criteria

Inclusion Criteria (Patients). To be eligible to enroll in the study, patients must attend one of the seven randomized clinics associated with the Alliance-affiliated health center Near North Health Service Corporation. They must also meet all of the following criteria: 1) age 21 and older; 2) English or Spanish speaking; 3) have received a new or changed prescription (i.e. had not been prescribed at Alliance within the previous two years) for one or more of our study medications (Table 1); 4) have a personal phone line (land or mobile).

Inclusion Criteria (Providers). To be eligible to complete the provider survey, providers must see patients at one of the three Near North clinics randomized to the intervention arm (Louise Landau, Komed Holman, Sunnyside).

Study medications. To select these drugs, we reviewed the top prescriptions ordered in 2013 by providers at Alliance FQHCs and selected those that have a Med Guide/REMS requirement. These drugs were reviewed by clinicians and pharmacists to ensure the list was comprehensive and appropriately reflects prescribing behaviors in the clinics. These drugs are diverse by class, indication, duration, side effects, route of administration, and potential for harm. Each has an FDA risk communication goal that presently is not being achieved.

Table 1.

STU#: 00201638

testosterone	escitalopram	sitagliptin and metformin
amiodarone	fluoxetine	exenatide
carbamazepine	paroxetine	liraglutide
divalproex	sertraline	pioglitazone
gabapentin	doxepin	rivaroxaban
lacosamide	imipramine	ciprofloxacin
lamotrigine	mirtazapine	levofloxacin
levetiracetam	colchicine	moxifloxacin
oxcarbazepine	emtricitabine and tenofovir	salmeterol
phenytoin	nevirapine	budesonide and formoterol
pregabalin	fenofibrate	fluticasone and salmeterol
topiramate	clopidogrel	celecoxib
valproic acid	alendronate	diclofenac
aripiprazole	risedronate	indomethacin
quetiapine	pimecrolimus	meloxicam
clonazepam	tacrolimus	sulindac
bupropion	amphetamine	dexlansoprazole
trazodone	methylphenidate	pantoprazole
desvenlafaxine	linagliptin	metoclopramide
duloxetine	saxagliptin	tamoxifen
venlafaxine	saxagliptin and metformin	varenidone
citalopram	sitagliptin	propylthiouracil

alprazolam	ibandronate	mometasone-formoterol
apixaban	lisdexamphetamine	nortriptyline
dexmethylphenidate	lorazepam	olanzapine
diazepam	lurasidone	tramadol
fluticasone-vilanterol		

Table 1 – part 2.

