9.1 Study design

We will conduct a 2-arm, randomized trial at one Alliance-affiliated federally qualified health center (FQHC) in Chicago, Near North Health Services Corporation, to evaluate the EMC2 intervention strategy compared to usual care.

We will assess patients' Rx knowledge and behavior at baseline, 4 weeks, and 3 months. Prevalence of ADEs and rate of their detection will be determined at 3 months or at an earlier interview if they state having already completed the course of medication. The fidelity and economic impact of the intervention will also be investigated via process and cost measures, in addition to patient and provider feedback. Results will determine effectiveness and identify any necessary modifications, guiding future dissemination efforts.

Study Arms:

Usual Care. Current usual care includes 1) variable physician and/or nurse counseling without any EHR notifications or counseling support; 2) no distribution of print medication information materials in Alliance clinics, and variable, limited distribution likely in pharmacies; 3) no active surveillance of medication use post-visits.

Intervention Arm: EMC2 Strategy. Following a patient's movement through a provider visit at one of the Near North clinics randomized to the intervention, the following five activities (described in more detail in 9.2) will occur:

- Provider counseling (prompted by provider medication alert)*
- Automated delivery of med guide summary*
- IVR follow-up phone assessment
- IVR lab report to clinic via EHR
- Nurse counseling (if warranted by lab report)

**Because the first two activities must occur at the time of the clinic visit, which is before we will have the opportunity to invite the participant to enroll in the study, those activities will occur for all patients prescribed a study medication at an intervention clinic, regardless of whether or not they subsequently enroll. (see last paragraph of 3.1)*

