9.2 Description of the intervention

1. Provider Medication Alert: If a prescribing clinician attempts to place a new order or change an existing prescription for one of the study medications (Table 1), an EHR-generated alert will notify the provider that the medication requires patient counseling. This alert will contain a brief description of the top risks or side effects that patients may experience while taking this medication; this information is directly derived from the FDA-approved Medication Guide for the drug. The pop-up will also include an html link to the 1-page Med Sheet, which they can use to further inform their counseling.

2. Automated Delivery of Med Guide Summary: When the patient leaves an encounter and checks out, the medication order in Centricity will automatically cue printing of the 1-page Med Guide Summary.

STU#: 00201638

3. IVR Follow-Up Phone Assessment: One day after a patient's baseline interview (which will occur within 1-30 days post-visit), the patient will be prompted to call into the automated IVR system. The goal of the IVR call is to confirm patients' understanding and safe use of the prescribed high-risk medication they are taking, and to screen for any adverse drug events that may arise from having taken the medicine.

The call will investigate content areas that will be standard across all medications under study: 1) medication recognition, 2) medication fill (and fill barriers, if applicable), medication adherence (and adherence barriers, if applicable), perceived effectiveness, and side effects experienced. The IVR content was derived from the Med Guide Summaries. Patients are able to speak their responses as "yes", "no", or "do not know" or use their keypad.

To facilitate the call, patients will be sent (via text or phone call) a call-in number for the IVR system so that they are able to make the call at their convenience. The text with the call-in number will be sent on the day following the patient's baseline interview. (The day lag is needed so that the participant's medication data can first be uploaded to the IVR system in preparation for the call).

If subjects have not used the system after one day, a reminder text message, again including the call-in number, will be sent by the RA at Northwestern. If subjects have not used the system after two days, the RA at Northwestern will call the patient to remind them to call into the system and to ensure they have the call-in details.

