9.3 Research procedures

Research activities will include a baseline interview and follow-up interviews at 4 weeks and 3 months; all interviews will be conducted over the phone. Patients in the intervention arm will receive a prompt to call into an interactive voice response (IVR) system one day after their baseline interview (so 2-45 days after their index clinic visit) to confirm understanding and safe use of their medicine (described in 9.2 Description of the Intervention).

Pilot Testing. We will pilot-test the study battery, protocol and patient materials among English and Spanish-speaking patients at Alliance sites. Cognitive interviews will be conducted among a convenience sample of 30 patients (n=15 per language) that meet full eligibility criteria. We will obtain average interview completion times, elicit patient comprehension, and acceptability of the interview and patient materials. Any identified problems will be analyzed and modifications made as appropriate. Pilot patient data will be used if no significant changes are made to the study.

STU#: 00201638

Initial Interview. After confirming patient eligibility, obtaining verbal consent, and receiving patient prescription information, the RA will administer the baseline interview via phone. As long as the patient is still taking or planning to take the prescribed medicine, the patient will then be eligible for follow-up interviews and, if in the intervention arm, to receive the remaining EMC2 components (IVR, nurse follow-up).

Follow-up Interview #1. The first follow-up interview will be scheduled at the time of the baseline interview for 4 weeks later.

Follow-up Interview #2. The second follow-up interview will be scheduled at the time of the 4-week interview for 8 weeks later.

Spanish Language Materials. All study materials (screener script, consent form, battery, IVR call) have been or will be translated into Spanish to accommodate Spanish speakers. Several of the measures in the battery already have validated Spanish versions; everything else has been translated by Research Support Services, led by [name], using a modified committee approach. In this translation approach, three bilingual, bicultural translators independently translate one-third of each document into Spanish, then discuss the resulting texts and reach an agreement on best words/phrases for the final product. The strength of this approach has been recognized by the Census Bureau Guidelines for Survey Translation.

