To account for the correlated nature of the data from participants at the same practice and multiple observations per patient, we will use GLMMs for analyses of all data, specifying identity link for continuous and the logit link for binary outcomes using PROC GLIMMIX in SAS (v.9.4). Treatment assignment by time will be the independent variable of primary interest and modeled as a fixed effect and practice location as a random effect, with additional subject statement to model correlations within patient. We will also include fixed effects for any potential confounding covariates noted in the descriptive studies. For all GLMM analyses we will report point estimates and 95% confidence

STU#: 00201638

intervals, and the extent to which random effects suggest correlation of outcomes within practice location. Additionally, we will estimate the ICCs for all outcomes to be used in future studies.

Aim 2 Analysis Plan: We will repeat all GLMM analyses described in Aim 1, but with the inclusion of a fixed effect for participants' literacy defined as limited (inadequate or marginal literacy) vs. adequate. We will formally test for differences in intervention effects according to literacy by including a literacy-intervention interaction term. Statistically significant interaction terms ($p < 0.05$) will indicate that the disparities in understanding between the intervention and usual care group vary by literacy level. Similar analyses will be used to test for interactions of intervention effects by age and English proficiency (using Census criteria of 'very well' vs. 'less than very well').

Aim 3 Analysis Plan: Following completion of enrollment, we will determine the extent to which the intervention was implemented as planned in the intervention arm. We will ask patients in the intervention arm if they were counseled, and whether they received the Med Guide Summaries and the post-visit IVR call. Bivariate analyses will be performed to compare relevant outcomes for H4-H7 between arms using t-tests, Wilcoxon Rank-Sum, or χ^2 tests, as appropriate. Aim 3 findings will also directly inform follow-up qualitative investigations in Aim 4.

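### The Aim 1 model makes arm-by-time the primary term without naming a contrast; read as change from a baseline taken after part of EMC2 was delivered, it is not the 3-month difference that was powered

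*Combined protocol and SAP*

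**What the plan says.** For Aim 1, section 11.1 specifies generalized linear mixed models with practice location as a random effect and within-patient correlation, and states: "Treatment assignment by time will be the independent variable of primary interest and modeled as a fixed effect". It gives no visit, contrast or coding for that term and does not say how the baseline interview enters the test.

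Other sections bear on what the test should be:

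- **Hypotheses (1.2).** H1 reads: "Patients receiving the EMC2 intervention will have better understanding of medication risks than those in the control arm". This is a difference in level and does not mention change.
- **Power (11.2).** The sample size rests on the between-arm comparison of knowledge at 3 months, by an independent t-test with variance inflation. Section 11.1 likewise counts the 960 patients retained at 3 months as the primary analysis set.
- **Assessments (9.1).** Patients are assessed on "knowledge and behavior at baseline, 4 weeks, and 3 months".
- **Delivery (3.1, 9.1).** Two of the five EMC2 activities, prompted counseling and the Med Guide Summary, precede enrolment: "the first two activities must occur at the time of the clinic visit".
- **Baseline timing (9.2, 9.3).** Section 9.2 places the baseline interview 1 to 30 days after the visit. Section 9.3 puts the IVR prompt, sent one day after baseline, at "2-45 days after their index clinic visit", which implies a baseline as late as day 44.
- **Measures (9.4).** Knowledge items are keyed to the Med Guide Summary, and the baseline interview is also where prescriber and nurse counseling is assessed.

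**The concern.** An analyst following section 11.1 would most naturally fit arm, time and their interaction with baseline as reference, and test the interaction. That tests the change in the arm difference after the baseline interview.

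In the intervention clinics, patients reach that interview having already been exposed to the in-clinic components, and the first knowledge score tests the content of the sheet they were due to receive. H1 and H2 concern the whole strategy. Under the interaction reading, an in-clinic gain that is present at baseline and persists contributes nothing to the test, and one that fades counts against EMC2. The trial could then report no effect on its first primary outcome despite a true 3-month difference, and the stated 80% power would not apply to the test performed.

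Two readings with different estimands also leave the primary test open to choice after the data are seen. Adverse drug event detection (H3), assessed once, is not affected.

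**Working it through.** **Inputs from section 11.2:** SD 28.4; 480 patients per arm at 3 months; 80 per location; ICC 0.001; difference 5.5 points; 5% type I error (taken as two-sided). Section 11.1 gives 6 locations per arm. Section 3.2 instead refers to "one of the three Near North clinics randomized to the intervention arm", out of seven clinics, so 3 v 4 is also shown.

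**Assumptions, not in the documents:** *f*, the share of the 3-month effect already present at the baseline interview; ρ, the within-patient correlation between baseline and 3 months.

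**Step 1. The plan's own figure.** The design effect is 1 + (80 − 1) × 0.001 = 1.079.

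- SE of the 3-month difference = 28.4 × √(2 × 1.079/480) = 1.904.
- Minimum detectable difference at 80% power = (1.960 + 0.842) × 1.904 = 5.33.
- Power at 5.5 = 82.3%.

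The stated 5.5 points at 80% is slightly conservative for these inputs. The calculation is a 3-month level comparison and contains no within-patient correlation.

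**Step 2. Change from baseline.** Assume complete pairs and a clinic effect that is stable over time and so cancels. The expected contrast is 5.5 × (1 − *f*), with SE = 28.4 × √(2(1 − ρ) × 2/480). Two-sided normal power:

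| ρ | SE | f = 0 | 25% | 50% | 75% | 100% |
|---|---|---|---|---|---|---|
| 0.3 | 2.169 | 71.8% | 47.7% | 24.5% | 9.7% | 5.0% |
| 0.5 | 1.833 | 85.1% | 61.4% | 32.3% | 11.7% | 5.0% |
| 0.7 | 1.420 | 97.2% | 82.8% | 49.1% | 16.2% | 5.0% |

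If the full design effect of 1.079 is kept, the ranges over ρ from 0.3 to 0.7 become 68.5% to 96.2% at *f* = 0 and 23.1% to 46.2% at *f* = 50%.

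**Step 3. Break-even.** The change test is weaker than the level test once *f* exceeds 1 − SE(change)/SE(level). With 6 v 6 locations and ICC 0.001:

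- ρ = 0.5: 1 − 1.833/1.904, about 4%.
- ρ = 0.7: 1 − 1.420/1.904, about 25%.
- ρ = 0.3: below zero, so the change test is weaker for any *f*.

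**Step 4. Few clinics.** Using a noncentral t with degrees of freedom equal to clinics minus 2 (10 or 5), and the level SE summed over arms with each arm's own cluster size:

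| Contrast, power for a 5.5-point effect | 6 v 6 | 3 v 4 |
|---|---|---|
| Level, ICC 0.001 (SE 1.904; 1.956) | 74.0% | 61.8% |
| Change, ρ = 0.5, f = 0 | 77.1% | 67.2% |
| Change, ρ = 0.5, f = 50% | 27.4% | 23.2% |
| Level, ICC 0.01, assumed (SE 2.453; 2.834) | 52.6% | 35.1% |

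At ICC 0.01 and ρ = 0.5, change is the stronger test until *f* exceeds about 25% (6 v 6) or 35% (3 v 4).

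**The case against.** The strongest reply is that the harmful reading is not the intended one. Section 11.1 speaks of an interaction term explicitly for Aim 2 and not for Aim 1. Aim 2 tests effect modification by literacy with a two-way literacy-by-intervention term; had the Aim 1 effect been arm-by-time, a three-way term would be expected. A single arm-by-time variable can also be fitted as arm-by-visit cell means, from which the 3-month difference is read directly. For knowledge, sections 11.1 and 11.2 already point to 3 months. Further, *f* and ρ are not in the documents, and across the grid the power runs from 5% to 97%, sometimes above that of the 3-month test.

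Most of this is fair, and it makes the 3-month contrast the more plausible intention. But no passage states it as the model test, and section 11.2 fixes the time point for the sample size only. For proper use (H2), the only time cue is the remark in section 11.2 on detectable differences at 3 months, written for the Aim 2 subgroups. The power figures show a possible loss and do not establish one.

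It can also be said that some patients have their final interview at baseline or 4 weeks (sections 7 and 22.4), so that a 3-month estimate relies on the model for them. That applies equally to a change-to-3-months contrast.

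**Conclusion.** The concern holds. Section 11.1 gives a rule for the primary term which, read in the usual way, tests a different quantity from the one in H1 and section 11.2, against a baseline that follows two of the five components.

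The harm is conditional on two things: that the interaction is what is tested, and that some effect is already present at the baseline interview. If half the 5.5-point effect is present, power is 24.5% to 49.1% for correlations 0.3 to 0.7, against 82% for the 3-month difference. If all of it is present and persists, the test has only its 5% error rate. If none is present, there is no loss at correlation 0.5 and a gain at 0.7.

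This should be fixed before analysis. Confidence is medium, because the size depends on two quantities that the documents do not give.

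**What to change.** In section 11.1, keep the same model with visit as a categorical factor (arm, visit, arm-by-visit) and add:

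- The primary contrast for knowledge (H1) is the model-estimated EMC2-minus-usual-care difference at 3 months. The same contrast on the logit scale is used for proper use (H2).
- The baseline-interview score is a post-intervention outcome. It is not used as a pre-treatment covariate, and the arms are not constrained to be equal at it.
- The arm differences at baseline and 4 weeks are secondary.
- The arm-by-visit terms are described only as the change in the arm difference after baseline. With two arms they mix any IVR or nurse effect with decay of the in-clinic gain, so they are not presented as the added effect of those components.

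The cost is a few sentences and one contrast statement, with no new data. The drawback is that a level contrast keeps chance differences between the few clinics, which a change score would remove if they are stable. On cluster degrees of freedom this gives 74% power (6 v 6) or 62% (3 v 4) at ICC 0.001, and less at a larger ICC. That price should be stated with the choice; it does not justify an estimand that can leave out the in-clinic components.

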11. DATA AND SPECIMEN MANAGEMENT

11.1 Data analysis plan

Aim 1 Analysis Plan. The proposed trial uses a cluster-randomized design where the practice location is the unit of randomization. We will randomize 12 locations to two arms (usual care, EMC2) resulting in 6 per arm. Locations will be matched by total number of patients eligible for the study as well as proportion of Spanish speaking patients, with one location from each pair randomized to each arm. We will accrue ~100 patients per location, on average, and conservatively anticipate ≥80% retention at 3-month follow-up. These estimates result in 1200 participants recruited with an anticipated 960 patients (480 per arm, 80 per location) available for primary data analysis.

Medication knowledge associated with high-risk medications is the first primary outcome of interest for Aim 1 (H1), and will be analyzed as a score ranging from 0-100 reflecting the percent of items correct for each medication. Medication use outcomes (proper use, adherence) and detection of ADEs are relevant to the other hypotheses of interest for Aim 1 (H2, H3). Associations between the outcomes and potential confounders at the patient (socio-demographic characteristics, comorbidities, # and type of medications taken, previous history with side effects, literacy, and primary language) and medication (drug type, route of administration) levels will be examined. We intend to use generalized linear mixed models (GLMM) to analyze the data, which can handle data that is missing at random (MAR). Additionally, we will examine rates of missing data, and determine if there are any discernible patterns using GLMMs with a logit link function to predict the presence of missing data. Should we find significant predictors, we will use multiple impute methods and present results as secondary analyses.

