11.2 Power analysis

The sample size for this study was based on comparisons of the primary outcome of medication knowledge between the two arms (i.e., usual care vs EMC2) at the 3-month interview. We expect

STU#: 00201638

participants in the usual care arm to score an average of 55.6 (SD=28.4) based on a previous study testing comprehension of the FDA standard Med Guides to those to be used in this study. Enrolling 1200 participants and estimating 80% retention at the follow-up interview (n=960, 480 per arm), we will have 80% to detect a minimum difference of 5.5 between the EMC2 and the usual care arm assuming a Type I error of 5%, assuming 100 patients per practice site enrolled at baseline and n=80 available at 3 month follow-up. This effect size was calculated based on an independent t-test with a variance inflation factor to account for the cluster-randomized design. An intra-class correlation coefficient (ICC) of 0.001 was used as we expect the clustering of practice site to have minimal influence on patient outcomes.

Usual care estimates for understanding of risks and demonstrated safe use outcomes were obtained from prior work. For subgroup analyses on these outcomes for Aim 2, we expect roughly 38% to have limited health literacy. Detectable differences at 3 months are based on estimates of 3 patients per provider with limited literacy and 5 with adequate literacy. Detection of ADEs is defined as the number of events recorded in the medical chart out of the total number reported by patients at the 3-month interview. In a study in which 20% of participants reported at least 1 adverse drug event, 35 of their 166 (21%) reported events were recorded in their medical chart. Therefore, the sample size calculation for this outcome was based on 21% of reported ADEs in 20% of our expected sample at 3 months (n=96 per arm, 3 patients per 32 providers, assuming an equal number of providers in each arm will have patients with no ADEs). We will be able to detect a minimum of 18.2 between the EMC2 and the usual care arm. For subgroup analyses by literacy, we assume 1 patient per provider with limited literacy and 2 with adequate literacy.

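### The arm-by-time effect named as primary has no between-clinic variation in its standard error, so its test is unprotected if clinics change differently between visits

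*Combined protocol and SAP*

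**What the plan says.** Section 11.1 states that "the practice location is the unit of randomization". For the Aim 1 model it then says: "Treatment assignment by time will be the independent variable of primary interest". That term is to be "modeled as a fixed effect and practice location as a random effect, with additional subject statement to model correlations within patient". The link is identity for continuous outcomes, which covers the knowledge score, and logit for binary ones. The section names no location-by-visit term, random slope, robust variance or degrees-of-freedom method.

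Section 11.2 points to a different contrast. It bases the sample size on "comparisons of the primary outcome of medication knowledge between the two arms (i.e., usual care vs EMC2) at the 3-month interview", computed from "an independent t-test with a variance inflation factor to account for the cluster-randomized design", with an ICC of 0.001.

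The number of clinics also differs. Section 11.1 has 12 locations, six per arm. Sections 3.2 and 19.1 have seven clinics, and section 3.2 names three as intervention clinics, which leaves four controls.

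**The concern.** In a cluster-randomised trial the standard error of the treatment effect should reflect how much the randomised units vary on the contrast being tested. If arm-by-time is a difference in change, a constant clinic effect enters both visits and subtracts out. What remains in the standard error is within-patient error, much as if patients had been randomised one by one. Clinics that differ in their average change add noise that this model has no term for.

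Such differences are plausible here. After baseline the remaining intervention components are the IVR call, the report to the clinic and nurse follow-up, and section 9.2 lets each clinic set its own response. Section 7 also ends follow-up for patients who stop or never take the drug, so the mix of patients at later visits may shift by clinic.

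At stake are the confidence interval and p-value of the effect that section 11.1 calls primary.

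**Working it through.** **The plan's own figure.** From section 11.2: SD 28.4, 480 per arm, 80 per site, ICC 0.001, 80% power, 5% error (taken as two-sided).

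- Design effect = 1 + 79 × 0.001 = 1.079.
- Detectable difference = (1.960 + 0.842) × 28.4 × √(2 × 1.079 / 480) = 5.34 points, against 5.5 stated.
- With 960/7 ≈ 137 per site, the design effect is 1.136 and the difference 5.47.

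The stated 5.5 is slightly conservative and plays no part in this point. It describes a difference in level at 3 months, not a difference in change.

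**Does the clinic intercept cancel?** Mixed models with a clinic random intercept and a patient effect were fitted by REML to simulated data (12 clinics, two visits).

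| Clinic SD | Clinic-by-visit SD | SE, arm at 3 months | SE, arm-by-time |
|---|---|---|---|
| 0 | 0 | 0.131 | 0.1237 |
| 0.2 | 0 | 0.190 | 0.1237 |
| 1 | 0 | 0.918 | 0.1237 |
| 3 | 0 | 2.824 | 0.1237 |
| 0.2 | 0.3 | 0.233 | 0.1266 |

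Clinic differences in level leave the arm-by-time standard error unchanged. Real clinic-by-visit variation barely moves it. The 3-month standard error responds to both.

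**Size of the effect on type I error.** Let ρ be the ICC at one visit, r the clinic correlation across visits, and 0.5 the within-patient correlation. The documents give only ρ = 0.001. The values of r, the 0.5 and ρ = 0.01 are assumptions. The calculation takes two visits and complete data.

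- ICC of change = ρ(1 − r) / [ρ(1 − r) + (1 − ρ) × 0.5]
- Design effect the model misses, DE = 1 + (m − 1) × ICC of change
- Actual error = 2[1 − Φ(1.96/√DE)]

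Worked case, ρ = 0.01 and r = 0.8: ICC of change = 0.002 / (0.002 + 0.495) = 0.00402.

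- 12 clinics, m = 80: DE = 1 + 79 × 0.00402 = 1.318; 1.96/1.148 = 1.707; error 8.8%.
- Seven clinics, m = 137: DE = 1 + 136 × 0.00402 = 1.547; 1.96/1.244 = 1.576; error 11.5%.

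| Clinics | ρ | r = 1 | r = 0.8 | r = 0.5 |
|---|---|---|---|---|
| 12 | 0.001 | 5.0% | 5.4% | 5.9% |
| 12 | 0.01 | 5.0% | 8.8% | 14.3% |
| 7 | 0.001 | 5.0% | 5.6% | 6.6% |
| 7 | 0.01 | 5.0% | 11.5% | 20.2% |

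Simulation of 20,000 trials per setting agrees. With 6 v 6 clinics of 80 it gave 5.4% and 6.0% at ρ = 0.001, and 9.0% and 14.5% at ρ = 0.01 (r = 0.8 and 0.5). With four control clinics of 120 and three intervention clinics of 160 it gave 5.8% and 6.9%, then 11.2% and 20.5%. With r = 1 and these two ICCs, error stayed at 4.9-5.0%. A two-sample t-test on clinic mean changes, with 10 or 5 degrees of freedom, stayed between 4.3% and 5.3% throughout.

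**The case against.** A reader might infer that the primary test is too liberal and that 5% is not held. The documents do not support that as a flat statement, for three reasons.

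- **Inflation needs clinic-by-visit variance, and the plan reports none.** If clinics differ only in level, the test is exact. At the plan's ICC the excess is at most about two percentage points, and the larger rates need an ICC ten times higher. Staffing or pharmacy changes are calendar events. With enrolment over two years, they meet different patients at different visits and partly average out. This stands, and it makes the point conditional. It does not remove it, because section 11.2 supports 0.001 only by an expectation of little clustering.
- **Arm-by-time may not be the contrast tested.** H1 in section 1.2 is a claim about level, and section 11.2 powers the 3-month difference. Two intervention components come before the baseline interview (section 9.1), so a pure change contrast would leave out benefit already present at baseline. Fitting treatment by time and reading off the 3-month difference fits all of this, and the clinic intercept does enter that standard error. This also stands. It shows that the primary contrast is unsettled, while the term section 11.1 calls primary is the unprotected one.
- **"Intercept only" is read from silence.** Section 11.1 says a random effect, not a random intercept. The plain reading is still an intercept, and no other clinic term is named. The cancellation is exact for the identity link with complete data and approximate for logit outcomes or with dropout.

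**Conclusion.** The point holds in conditional form. As section 11.1 reads, the arm-by-time standard error contains no between-clinic variation, so the test is not protected against clinics changing differently between visits. There is no inflation if clinics differ only in level. With within-patient correlation 0.5 and clinic correlation across visits 0.8 to 0.5, both assumed, error is about 5-7% at the plan's ICC of 0.001. At an assumed ICC of 0.01 it is about 9-14% with 12 clinics and 12-20% with seven. If the 3-month arm difference is the primary test, the understatement is much smaller. The omission should be repaired, because it concerns a stated analysis rule that can give too narrow an interval. Its actual size cannot be known from the documents.

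**What to change.** In section 11.1:

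1. State which contrast is primary, the 3-month arm difference that section 11.2 powers or arm-by-time.
2. If arm-by-time is kept, test it on clinic-level mean changes with t degrees of freedom from the number of clinics. This held close to 5% in every setting run. Alternatively, add a location-by-visit random effect together with a small-sample degrees-of-freedom method.
3. Reconcile 12 and seven clinics across sections 3.2, 11.1, 11.2 and 19.1, since fewer clinics make the problem worse.

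The random effect is not enough alone. In 6,000 simulated trials with three v four clinics, r = 0.8 and a normal reference, error was still 6.9% at ICC 0.01. The added variance was estimated as zero in 35% of those trials, which returns the original standard error. With t on 5 degrees of freedom the same model was conservative (0.7-2.9% for ICC 0.001 to 0.02).

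The edit is short, but intervals widen and some power is lost. With seven clinics the critical value is 2.57 on 5 degrees of freedom against 1.96, so intervals are about 31% wider (2.57/1.96 = 1.31) before any added variance. With 12 clinics it is 2.23 on 10 degrees of freedom, about 14% wider (2.23/1.96 = 1.14).
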